#### Proportion of Patients With Endoscopic Improvement at Week 6:

A patient will have experienced endoscopic improvement at Week 6 if the change from baseline (the last assessment prior to the first dose of study drug) to Week 6 (Visit 6) in the modified UCDAI mucosal appearance score is  $\leq -1$ , where change is computed as the Week 6 score minus the baseline score.

Missing data will not be imputed at Week 6 if a patient has not made it to Week 6 and/or has no Week 6 mucosal appearance result.

The proportion of patients with endoscopic improvement at Week 6 will be summarized and analyzed using methodology similar to the primary efficacy endpoint for both the ITT and PP populations. A bar chart of percentage of patients with endoscopic improvement at Week 6 by treatment group will be presented.

Change in Symptoms (Rectal Bleeding and Stool Frequency) From Baseline to Each Study Visit:

Rectal bleeding is scored at each visit as normal (none), mild (streaks of blood), moderate (obvious blood), or severe (mostly blood). Stool frequency is scored at each visit as normal (none), mild (1-2 stools more than usual per day), moderate (3-4 stools more than usual per day), or severe ( $>4$  stools more than usual per day).

The number and percentage of patients with each categorical result will be presented for each symptom (rectal bleeding and stool frequency) at baseline (the last assessment prior to the first dose of study drug) and each post baseline visit for ITT and PP populations. Each IBD98-M group will be compared to placebo at each visit using Fisher's exact test.

A shift table will be prepared for each symptom, showing the number and percentage of patients with normal, mild, moderate, and severe results at baseline versus normal, mild, moderate, and severe results at each post-baseline visit, by treatment group.

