### Secondary

- To compare clinical improvement rates at Week 6 among treatment groups (defined as a  $\geq 3$  point reduction from baseline in the modified UCDAI score)
- To compare endoscopic improvement at Week 6 among treatment groups (defined as a  $\geq 1$  point decrease from baseline in modified UCDAI mucosal appearance subscore)
- To determine the change in symptoms (rectal bleeding and stool frequency) from baseline to each study visit among treatment groups
- To evaluate the safety and tolerability profile of IBD98-M

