Patients should be encouraged to take their medication at the same time 30-120 minutes before meals every day. During the study, patients will visit the clinic on 7 occasions: 2 visits during the screening period (the second screening visit is the baseline visit); 4 visits during the treatment period at weeks 0, 2, 4, and 6; and an end-of-study/withdrawal visit at week 8, concluding the follow-up period. Patients will record symptoms in a daily diary starting 7 days before treatment and continuing until the end-of treatment period (Visit 6). For the baseline scoring of rectal bleeding and stool frequency items, the worst score from the previous 7 days of diary data before the randomization visit will be used excluding the day of and the day after endoscopy, as well bowel preparation for endoscopy where applicable.

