## 6. STATISTICAL CONSIDERATIONS

For efficacy and safety data, descriptive statistics (n, mean, standard deviation [SD], median, minimum, and maximum for continuous data, and n [%] for categorical data) will be presented. Similarly, wherever applicable, changes from baseline will be summarized in the same manner.

Unless otherwise stated, the denominator for percentages will be based on the number of patients in each treatment group who provided non-missing responses to the categorical variable, all statistical tests will be two-sided and at the 5% level of significance, and all differences between treatment groups will be presented with two-sided 95% confidence intervals (CIs). All p-values will be displayed to three decimals and rounded using standard scientific notation (e.g., 0.XXX). If a p-value less than 0.001 occurs it will be shown in tables as <0.001. If a p value greater than 0.999 occurs it will be shown in the tables as >0.999.

Unless otherwise stated, percentages will be presented to one decimal place in all summaries.

Minimum and maximum values will be presented to the same number of decimal places as collected on the case report form (CRF) or within the laboratory panel; mean and median will be presented to one decimal place more than CRF data; standard deviation will be presented to two decimal places more than CRF data.

Dates will be presented in format DDMMYY and numbering for tables, figures, and listings will follow ICH E3.

All statistical analyses will be performed using Statistical Analysis System (SAS®) version 9.4 or higher (SAS Institute, Cary, NC).

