### 7.8.2 Secondary Efficacy Endpoint and Analyses

The secondary efficacy endpoints include:

Proportion of patients with clinical improvement at Week 6 (defined as a  $\geq 3$  point reduction from baseline in the modified UCDAI score)

Proportion of patients with endoscopic improvement at Week 6 (defined as a  $\geq 1$  point decrease from baseline in modified UCDAI mucosal appearance subscore)

Change in symptoms (rectal bleeding and stool frequency) from baseline to each study visit

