#### Proportion of Patients With Clinical Improvement at Week 6:

The modified UCDAI score system includes four variables, namely rectal bleeding, stool frequency, mucosal appearance, and the physician's global assessment of disease activity. Each variable is scored from 0 – 3 so that the total score (a summation of the 4 variable scores) ranges from 0 – 12, with higher scores indicating more severe disease.

A patient will have experienced clinical improvement at Week 6 if the change from baseline (the last assessment prior to the first dose of study drug) to Week 6 (Visit 6) in the modified UCDAI score is  $\leq -3$ , where change is computed as the Week 6 modified UCDAI score minus the baseline modified UCDAI score. Only patients with a modified UCDAI score at baseline and Week 6 will have their clinical improvement status determined (no non-responder imputation).

The proportion of patients with clinical improvement at Week 6 will be summarized and analyzed using methodology similar to the primary efficacy endpoint for both the ITT and PP populations. A bar chart of the percentage of patients with clinical improvement at Week 6 by treatment group will be presented.

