### **7.8.3 Exploratory Endpoint**

The exploratory endpoint is the reduction in fecal calprotectin.

Fecal calprotectin will be collected at Visit 3 (Week 0) and Visit 6 (Week 6) or early termination. Change from Visit 3 to Visit 6 or early termination will be computed as the Visit 6 value minus the Visit 3 value. Descriptive statistics (n, mean, standard deviation (SD), median, minimum,

and maximum) will be presented for observed fecal calprotectin at each visit and for change from Visit 3 at Visit 6 by treatment group for the ITT and PP populations.

Change from Visit 3 to Visit 6 in the fecal calprotectin will be analyzed as the response variable in an analysis of covariance (ANCOVA) model to compare each of the IBD98-M groups versus placebo. The model will include treatment as a fixed effect and the Visit 3 fecal calprotectin value as a covariate. The treatment-by-baseline interaction will be included in the model and if the term is not significant at the 0.10  $\alpha$ -level, it will be excluded from the model. If the interaction is significant at the 0.10  $\alpha$ -level, the interaction will be investigated and appropriate interpretation made or appropriate alternative methodology identified and implemented. Least squares means and associated 95% confidence intervals will be estimated for each treatment group, and the least squares mean difference (each IBD98-M group minus placebo) and associated 95% confidence interval will be estimated for each IBD98-M treatment group. Least square means will be compared between each active treatment group and placebo using two-sided testing at the  $\alpha = 0.05$  level. There will be no multiplicity adjustment.

The residuals from the above analyses will be checked for normality and homogeneity of variance. Normality will be examined by normal probability plots, while homogeneity of variance will be assessed by plotting the residuals against the predicted values for the model. Any deviation from either assumption may result in further analysis using an appropriate alternative transformation (such as logarithmic or power transformation) of the data or an alternative appropriate statistical analysis.

The analysis of the above exploratory efficacy endpoint will be repeated for the PP population.

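### Symptom change from baseline is a secondary endpoint, but its only between-group analysis is Fisher's exact test on visit grades; one baseline-adjusted difference with a 95% CI should be added

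*SAP*

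**What the plan says.** The secondary objective in SAP Section 2 is "To determine the change in symptoms (rectal bleeding and stool frequency) from baseline to each study visit among treatment groups", and SAP 7.8.2 lists the matching endpoint: "Change in symptoms (rectal bleeding and stool frequency) from baseline to each study visit". Each symptom has four ordered grades, normal to severe, scored 0 to 3.

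Under the symptom subheading, 7.8.2 plans three outputs:

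- counts and percentages of each grade at baseline and at each later visit;
- a test: "Each IBD98-M group will be compared to placebo at each visit using" Fisher's exact test, with the table layout not stated;
- a shift table of baseline grade against visit grade, by arm.

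Section 6 adds two general rules: "all differences between treatment groups will be presented with two-sided 95% confidence intervals", and, for descriptive summaries, "wherever applicable, changes from baseline will be summarized in the same manner". Protocol 12.4.1 gives no method for symptom change; its rule for secondary endpoints covers only remission and improvement.

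The exploratory calprotectin endpoint in SAP 7.8.3 is handled differently. There, "The model will include treatment as a fixed effect and the Visit 3 fecal calprotectin value as a covariate", and each dose gets an adjusted difference from placebo with a 95% CI.

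**The concern.** The objective asks how symptom change differs between arms. The only output that compares arms looks at where patients are at a visit and ignores where they started: a patient who went from severe to normal and one who went from mild to normal count the same. The only outputs that use baseline, the shift tables and any change summaries, are within arm. The reader would get a p-value for whether grade distributions differ, but no named size of the difference in change and no interval for it. With 17 patients per arm in an exploratory trial, size and uncertainty are the more useful result. At stake is the usefulness of one unadjusted secondary endpoint.

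**Working it through.** **The plan's own figure.** The documents give no power or effect size for symptoms. The 17 per arm comes from the remission endpoint. With true rates 0.38, 0.20 and 0.20 and ties broken at random, the exact probability that the best arm ranks first is 0.8004 at 17 per arm, and 17 is the smallest size reaching 0.80. The figure reproduces as a selection-design number. It carries no power statement for visit-wise tests.

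**What the planned test reports.** Take made-up grade counts (normal/mild/moderate/severe) of 8/5/3/1 on a dose and 3/5/5/4 on placebo.

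- Fisher on the 2×4 table, the natural reading, gives p = 0.219, and still 0.219 after the grade columns are shuffled. It uses neither grade order nor baseline.
- The mean scores are (5×1 + 3×2 + 1×3)/17 = 14/17 = 0.82 and (5×1 + 5×2 + 4×3)/17 = 27/17 = 1.59. The difference, −13/17 = −0.76 points, is nowhere asked for.

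**Assumptions for power.** Placebo at the visit 25/35/25/15%; baseline 5/30/45/20%; baseline-to-visit correlation 0.3, 0.5 or 0.7; 17 per arm; one dose against placebo; two-sided 5%. None of the distributions or correlations is in the documents. The odds ratio 2.45 is borrowed from the remission planning rates: (0.38/0.62)/(0.20/0.80) = 0.613/0.25 = 2.45.

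**True mean differences.** The mean of a 0-3 score is the sum of P(score > k) for k = 0, 1, 2.

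- Placebo: 0.75 + 0.40 + 0.15 = 1.30.
- Odds ratio 4: cumulative odds 0.333, 1.5 and 5.667 become 1.333, 6 and 22.67, so the mean is 0.429 + 0.143 + 0.042 = 0.614 and the difference is −0.69.
- Odds ratio 2.45: odds 0.817, 3.675 and 13.88, so the mean is 0.551 + 0.214 + 0.067 = 0.832 and the difference is −0.47.
- 30 points moved to normal from all abnormal grades: 1.30 × 0.45/0.75 = 0.78, difference −0.52.
- 30 points moved from mild to normal: −0.30.

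**Methods compared.** Fisher 2×4 by full enumeration (1,140 × 1,140 outcome pairs). Plain ANCOVA, change = intercept + treatment + baseline score, by simulation (10,000 trials per cell, Monte Carlo error at most 0.005).

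| Effect assumed | True difference | Fisher | Plain ANCOVA, correlation 0.3 / 0.5 / 0.7 |
|---|---|---|---|
| None | 0 | 4.7% | 5.0 / 5.0 / 5.0% |
| Odds ratio 2.45 | −0.47 | 17.7% | about 30-40%, rising with correlation |
| Odds ratio 4 | −0.69 | 38.8% | 56.0 / 62.5 / 71.6% |
| All abnormal to normal, +30 points | −0.52 | 30.0% | 33.5 / 36.1 / 43.0% |
| Mild to normal, +30 points | −0.30 | 52.6% | 13.7 / 13.4 / 16.6% |

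**Does the interval work on a four-grade score?** Coverage of the nominal 95% CI was 94.4-95.3% across all cells run, including other placebo distributions and 14 evaluable patients per arm. At odds ratio 4 the median half-width was 0.63, 0.59 and 0.53 points. As a check, the score variances are 1.01 on placebo and 0.69 on the dose, so the unadjusted half-width is about 2.04 × √((1.01 + 0.69)/17) = 0.64, and the adjusted values lie below it.

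**Can 7.8.3 be copied as it stands?** No. It tests treatment-by-baseline interaction at 0.10 and allows another method if that is significant or if residual plots look poor. Under these assumptions the interaction test fires in about 7-16% of trials. The coverage above is for the model without these steps.

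**The case against.** The strongest reply is that nothing here is wrong. Fisher's test keeps its size, the trial is exploratory, no multiplicity claim is made, and the shift tables do show change. Remission requires symptom scores of 0, so movement into the normal grade is arguably the pattern that matters most, and there the ANCOVA gains little or loses heavily. All of this stands. A reader might infer that the planned test is invalid or should be replaced; the documents and the figures support neither.

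A reader might also infer that Section 6 leaves no difference to which a CI could attach. That goes too far. Differences in the percentage in each grade could each carry one, and the primary endpoint relies on the same general rule. What remains is that 7.8.2 does not say which difference is meant, and a grade percentage at a visit is still not change.

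Finally, a reader might infer that the documents define several conflicting baselines. SAP Section 5 and 7.8.2 say which assessment is baseline (the last before first dose), while Section 3 says how diary items are scored: "the worst score from the previous 7 days of diary data before the randomization visit will be used". These can coexist. The three-day diary rule in Protocol 10.1 may be superseded: the SAP cites a protocol section on re-screening that the supplied protocol lacks. The SAP's own worst-score rule and the averaging note in its Appendix 17.1 do need reconciling, but that is a separate scoring question, which matters here because it supplies the covariate.

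**Conclusion.** The point holds as a suggestion for improvement. The stated endpoint is change compared between arms, and the plan contains no between-group estimate of that change. This mismatch follows from the text alone and needs no assumed distribution. The power figures all rest on assumed grade distributions and correlations. They favour the adjusted analysis for shifts across the whole scale (odds ratio 4: about 56-72% against 39%) and favour Fisher when change is confined to adjacent grades (mild to normal: about 13-17% against 53%). Power is therefore a reason to keep both analyses. The firm gain is a baseline-adjusted effect size with its uncertainty, from data already collected. No primary conclusion or decision rule depends on it.

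**What to change.** Add one paragraph to SAP 7.8.2:

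- For each symptom and each post-baseline visit, estimate the adjusted mean difference in change on the 0-3 score for each dose against placebo, with its 95% CI and p-value, from an ANCOVA with treatment and that symptom's baseline score. Treating the grades as numbers is consistent with the SAP, which already forms the total as "a summation of the 4 variable scores".
- State that the interaction pretest and the residual-based switching of 7.8.3 do not apply.
- Keep Fisher's test and state its table layout. Keep the frequency and shift tables.
- Use the baseline that 7.8.2 already names, and state the single rule by which its diary items are scored, after reconciling the worst-of-7-days rule with the averaging note.

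The cost is one paragraph and standard SAS code, with no new data. With symptom scores at Visits 4, 5 and 6 it adds 2 symptoms × 3 visits × 2 doses = 12 estimates per analysis population, with no multiplicity adjustment, as elsewhere in the plan. The downsides are that the model treats the grades as equally spaced, that baseline adds little when its correlation with the visit score is near 0.3, and that power is lower than Fisher's when change is confined to adjacent grades, which is why Fisher's test is kept.

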### **7.8.3 Exploratory Endpoint**

The exploratory endpoint is the reduction in fecal calprotectin.

Fecal calprotectin will be collected at Visit 3 (Week 0) and Visit 6 (Week 6) or early termination. Change from Visit 3 to Visit 6 or early termination will be computed as the Visit 6 value minus the Visit 3 value. Descriptive statistics (n, mean, standard deviation (SD), median, minimum,

and maximum) will be presented for observed fecal calprotectin at each visit and for change from Visit 3 at Visit 6 by treatment group for the ITT and PP populations.

Change from Visit 3 to Visit 6 in the fecal calprotectin will be analyzed as the response variable in an analysis of covariance (ANCOVA) model to compare each of the IBD98-M groups versus placebo. The model will include treatment as a fixed effect and the Visit 3 fecal calprotectin value as a covariate. The treatment-by-baseline interaction will be included in the model and if the term is not significant at the 0.10  $\alpha$ -level, it will be excluded from the model. If the interaction is significant at the 0.10  $\alpha$ -level, the interaction will be investigated and appropriate interpretation made or appropriate alternative methodology identified and implemented. Least squares means and associated 95% confidence intervals will be estimated for each treatment group, and the least squares mean difference (each IBD98-M group minus placebo) and associated 95% confidence interval will be estimated for each IBD98-M treatment group. Least square means will be compared between each active treatment group and placebo using two-sided testing at the  $\alpha = 0.05$  level. There will be no multiplicity adjustment.

The residuals from the above analyses will be checked for normality and homogeneity of variance. Normality will be examined by normal probability plots, while homogeneity of variance will be assessed by plotting the residuals against the predicted values for the model. Any deviation from either assumption may result in further analysis using an appropriate alternative transformation (such as logarithmic or power transformation) of the data or an alternative appropriate statistical analysis.

The analysis of the above exploratory efficacy endpoint will be repeated for the PP population.

## **7.9 Safety Data Endpoints and Analyses**

The safety endpoints include:

Treatment-Emergent Adverse Events (TEAEs)

Serious Adverse Events (SAEs)

Physical examination findings

Vital signs

Clinical laboratory parameters (including chemistry, hematology, coagulation, and urinalysis)

Electrocardiograms (ECGs).

Safety analyses will be performed on the safety population. Results will be reported by each treatment group and overall.

### 7.9.1 Adverse Events

All reported Adverse Event (AE) verbatim terms will be coded using the MedDRA dictionary version 17.0 or higher to provide the body system and preferred term.

A TEAE is defined as an adverse event that starts on or after the date of first dose of study medication. If the start date of an adverse event is incomplete or missing, the event will be assumed to be a TEAE, unless the incomplete start date (month and/or year) or the stop date (complete or incomplete) clearly indicates that the event started prior to dosing. Duration of the AE will be calculated in days as (AE stop date – AE start date) + 1, and will be calculated only for those events with both a complete start and stop date.

The relationship of each AE to study drug will be recorded as unrelated, unlikely, possibly, probably, and definitely. If a relation is missing for an AE, the relation of the event to study drug will conservatively be assumed to be definitely for summarization.

The severity of each AE will be classified as mild, moderate, or severe. If the severity of an AE is missing, the severity of the event will conservatively be assumed to be severe for summarization.

Number of events (e), number of patients (n) having an event, and percentage of safety patients (%) having an event will be presented by treatment group and overall for all AE and TEAE summary tables.

An overall summary of AEs and TEAEs will summarize the number of events, and the number and percentage of patients with events by treatment group and overall for the safety population.

The following categories will be included in this overall summary:

- at least one AE
- at least one related AE
- at least one SAE

- at least one related SAE
- at least one severe AE
- at least one TEAE
- at least one TEAE leading to discontinuation of study drug
- at least one related TEAE
- at least one related TEAE leading to discontinuation of study drug
- at least one serious TEAE
- at least one related serious TEAE
- at least one severe TEAE
- at least one related severe TEAE

TEAEs will be summarized by system organ class and preferred term for each treatment group and overall for the safety population. Multiple instances of an AE in each system organ class and multiple occurrences of the same preferred term will be counted only once per patient. The table will be sorted in alphabetical order by system organ class and in decreasing frequency of preferred terms based on total number of patients reporting the event within each system organ class. The denominator used for calculating the percentages will be the total number of patients included in the safety population for each treatment or overall. The following groups of events will be summarized in this manner:

- TEAEs
- Serious TEAEs
- TEAEs leading to study drug discontinuation or withdrawal from study
- Serious TEAEs leading to study drug discontinuation or withdrawal from study

- TEAEs by body system, preferred term ,and worst relationship (multiple occurrences at the body system or preferred term level will be counted only once per patient at the worst relation [related], all events will be counted at each level of relationship)
- Serious TEAEs by body system, preferred term, and worst relationship
- TEAEs by body system, preferred term, and maximum severity (multiple occurrences at the body system or preferred term level are counted only once per patient at the maximum severity, all events will be counted at each level of severity)
- Serious TEAEs by body system, preferred term, and maximum severity

All AEs will be listed.

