### **7.3 Withdrawal, Removal, and Replacement of Patients**

At any time, a patient's participation in the study may be terminated at his/her request or on the basis of the Investigator's clinical judgment. The reason for patient withdrawal will be noted on the electronic case report form (eCRF).

A patient may be discontinued from the study for the following medical or administrative reasons:

- Occurrence of an AE that in the judgment of the Investigator suggests an unacceptable risk to the patient
- Development of any condition on-study that, in the opinion of the Investigator or the Sponsor, places the patient at an unacceptable medical risk if he/she continues
- Pregnancy
- Patient request
- Institution of additional medical (rescue) therapy for UC. Rescue medication will not be permitted during the 6-week double-blind treatment period, and patients considered as treatment failures will be withdrawn and assigned an appropriate alternative UC treatment by the Investigator.

The Investigator may discontinue individual patients from the study at any time. Patients will be encouraged to complete the study; however, they may voluntarily withdraw at any time. The date of and reason for study discontinuation must be recorded on the eCRF regardless of the reason for withdrawal; all patients will be asked to undergo an end-of-study/early termination evaluation. Every attempt will be made to obtain all of the end-of-study assessments, including all of the subscales

of the UCDAI (i.e., stool frequency, bleeding, physician's assessment, and sigmoidoscopy score).

This study may be terminated at the discretion of the Sponsor or any regulatory agency. An Investigator may elect to discontinue or stop the study at his or her site for any reason, including safety or low enrollment.

In the event that a patient discontinues prematurely from the study due to a TEAE or serious TEAE, the TEAE or serious TEAE will be followed until it resolves (returns to normal or baseline values) or stabilizes, or until it is judged by the Investigator to be no longer clinically significant.

Patients who withdraw or are withdrawn may not re-enter the study and will not be replaced under this protocol.

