#### AE Reporting

Patients will be instructed to report AEs at each study visit. All AEs are to be followed until resolution or until a stable clinical endpoint is reached.

Each AE is to be documented on the CRF with reference to date of onset, duration, frequency, severity, relationship to study drug, action taken with study drug, treatment of event, and outcome. Furthermore, each AE is to be classified as being serious or non-serious. Changes in AEs and resolution dates are to be documented on the eCRF.

For the purposes of this study, the period of observation for collection of AEs extends from the time the patient gives informed consent until the follow-up visit (Visit 7). Follow-up of the AE, even after the date of therapy discontinuation, is required until the event resolves or stabilizes at a level acceptable to the Investigator.

Specific guidelines for classifying AEs by intensity and relationship to study drug are given in Table 4 and Table 5.

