DEFINITELY: This category applies to those AEs that the investigator feels are incontrovertibly related to test drug. An AE may be assigned an attribution of definitely related if or when it meets all of the following criteria: (1) it follows a reasonable temporal sequence from administration of the drug; (2) it could not be reasonably explained by the known characteristics of the patient's clinical state, environmental or toxic factors, or other modes of therapy administered to the patient; (3) it disappears or decreases on cessation or reduction in dose and recurs with re-exposure to drug (if rechallenge occurs); and (4) it follows a known pattern of response to the test drug.

When changes in the intensity of an AE occur more frequently than once a day, the maximum intensity for the event should be noted. If the intensity category changes over a number of days, then those changes should be recorded separately (with distinct onset dates).

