#### **SAE Reporting**

An SAE occurring during the study or within 2 weeks of stopping the treatment must be reported to the inVentiv Health Clinical Pharmacovigilance Group and will be communicated to the Sponsor. Any such SAE due to any cause, whether or not related to the study drug, must be reported within 24 hours of occurrence or when the Investigator becomes aware of the event. The investigator should report any SAE occurring after these time periods that is believed to be related to study drug or

protocol-specific procedures. Notification can be made using the dedicated fax line or telephone line for the inVentiv Health Clinical Pharmacovigilance Group:

inVentiv Health Clinical Pharmacovigilance [contact]

inVentiv Health Clinical Pharmacovigilance [contact]

If the Investigator contacts the inVentiv Health Clinical Pharmacovigilance Group by telephone, then a written report must follow within 24 hours and is to include a full description of the event and sequelae in the format detailed in the SAE reporting form.

The event must also be recorded on the standard AE eCRF. Preliminary reports of SAEs must be followed by detailed descriptions later on, including clear and anonymized photocopies of hospital case reports, consultant reports, autopsy reports, and other documents when requested and applicable. SAE reports must be made whether or not the Investigator considers the event to be related to the investigational drug.

Appropriate remedial measures should be taken to treat the SAE, and the response should be recorded. Clinical, laboratory, and diagnostic measures should be employed as needed in order to determine the etiology of the problem. The Investigator must report all additional follow-up evaluations to the inVentiv Health Clinical Pharmacovigilance Group within 10 calendar days. All SAEs will be followed until the Investigator and Sponsor agree the event is satisfactorily resolved.

Any SAE that is not resolved by the end of the study or upon discontinuation of the patient's participation in the study is to be followed until it either resolves, stabilizes, returns to baseline values (if a baseline value is available), or is shown to not be attributable to the study drug or procedures.

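### SAP 7.9.1 classifies TEAEs by start date alone while the protocol restarts the onset date when intensity changes over days, so an easing pre-dose AE can count as treatment-emergent and one AE as several events

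*SAP*

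**What the plan says.** The SAP (7.9.1, Adverse Events) gives a one-line rule: "A TEAE is defined as an adverse event that starts on or after the date of first dose of study medication". For unclear dates it adds: "If the start date of an adverse event is incomplete or missing, the event will be assumed to be a TEAE", unless the available dates clearly show onset before dosing. It computes duration as stop date minus start date plus 1. All AE and TEAE tables show the number of events (e) as well as patients (n, %). A patient with repeated occurrences of a term is counted once, at maximum severity in the severity tables, but every event is counted at its own severity level.

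The protocol (11.8.1, AE Reporting) says that "the period of observation for collection of AEs extends from the time the patient gives informed consent until the follow-up visit (Visit 7"). In the text after Table 5 it gives two rules for changing intensity. For rapid fluctuation: "When changes in the intensity of an AE occur more frequently than once a day, the maximum intensity for the event should be noted". For slower change: "If the intensity category changes over a number of days, then those changes should be recorded separately (with distinct onset dates"). The second rule does not distinguish worsening from easing.

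Protocol 12.5 says that when a patient has the same AE more than once, the summary tables use the occurrence with the greatest severity and closest association with study drug. Neither document says how separate records of one AE are to be linked for analysis.

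**The concern.** A start-date rule works when each AE has one record and one onset. Here the protocol gives a continuing AE a fresh onset date when its intensity changes over days. If the SAP rule is applied record by record, the later record passes the test even when the event began before any study drug was taken and is resolving. Worsening of a pre-dose AE is rightly captured in this way, but improvement is captured too.

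Incidence and severity of TEAEs is a named safety endpoint (Protocol 5.2.2), and the safety and tolerability profile is a secondary objective (Protocol 5.1). Small arms make each wrongly classified patient visible in the percentages. The result also sits badly with the protocol's own idea of an AE, under which a condition already present at screening qualifies only if it worsens.

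**Working it through.** The plan states no figure on this point, so there is nothing to reproduce. The check applies the written rules to constructed examples. Days are on the protocol's scale, with first dose on Day 0.

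**Inputs**
- TEAE test: record start on or after first dose (SAP 7.9.1).
- Splitting: a new record with a new onset date when intensity changes over days (Protocol 11.8.1, after Table 5).
- Counting: n once per patient; e counts every event (SAP 7.9.1).
- Arm size: 17 (SAP 3.3).

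**Step 1. Which records pass the test?** The alternative rule counts first onset on or after dosing, or a rise above the last pre-dose intensity.

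| Course of one AE | TEAE records, SAP rule | Patient counted, SAP rule | Patient counted, alternative rule |
|---|---|---|---|
| Severe Day -3, moderate Day 2, mild Day 4 | 2 | yes | no |
| Mild Day -3, severe Day 2 | 1 | yes | yes |
| Mild Day -3, no later change | 0 | no | no |
| Severe Day -5, mild Day -2 | 0 | no | no |
| Mild, first onset Day 3 | 1 | yes | yes |

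The two rules differ only in the first row, the easing event. Counting once per patient does not remove that patient: the pre-dose record is not a TEAE, so the post-dose records are the only ones left to count. The patient would enter the severity table as moderate.

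**Step 2. Event counts.** A post-dose AE that goes mild, moderate, mild over days has three records and adds 3 to e. A course of mild, moderate, severe, moderate, mild adds 5. Linked, each adds 1.

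**Step 3. Duration.** In the first row, suppose the moderate record is closed on Day 3, the day before the mild record opens. Its duration is (3 − 2) + 1 = 2 days, although the AE has by then lasted (3 − (−3)) + 1 = 7 days.

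**Step 4. Size per patient.** One misclassified patient changes an arm's TEAE incidence by 1/17 = 0.059, or 5.9 percentage points.

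**Step 5. How long is the exposed period?** Visit 1 falls between Days -28 and -7 in the supplied protocol (Table 2) and between Days -14 and -7 in the SAP (Table 1). The nominal period in which a pre-dose AE could arise is therefore up to 28 days under one and up to 14 under the other.

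**The case against.** The best defence is that the SAP speaks of an adverse event that starts on or after first dose, and on a plain reading an event that began earlier did not start then. The clause on incomplete dates points the same way, since it leaves out events that clearly began before dosing. The eCRF is not supplied; it may tie split rows together under one AE identifier. This makes the outcome uncertain, but does not settle it: the protocol gives the later record a distinct onset date, and no SAP rule tells the programmer to look past it.

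Several limits on the concern stand:
- Splitting does not follow every intensity change. Changes more often than once a day are recorded at the maximum.
- The easing problem is confined to AEs between consent and first dose.
- Repeated counting within one post-dose AE affects e, not n. No planned table summarises AE duration, so the shortened durations appear only in listings.
- All AEs are listed, so each case can be traced.
- The SAP follows Protocol Amendment 3 (SAP 1) and cites a protocol section on re-screening that the supplied protocol lacks. The governing splitting rule may differ.

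A reader might go further. The TEAE definition has no end date, and Protocol 7.3 says that "patients considered as treatment failures will be withdrawn and assigned an appropriate alternative UC treatment by the Investigator". It is tempting to infer that events long after withdrawal are wrongly charged to the assigned arm, that the protocol's own limit is two weeks after last dose, and that IBD98-M therefore looks safer. The documents do not support this:
- The SAE rule reads: "An SAE occurring during the study or within 2 weeks of stopping the treatment must be reported". The two conditions are alternatives. A patient who stops drug on Day 7 and is followed to Visit 7 on Day 56 is still in the study throughout those 56 − 7 = 49 days, so an SAE then lies inside the rule.
- Routine AE collection ends at Visit 7, nominally 56 − 42 = 14 days after treatment for completers. A longer tail needs an early withdrawal who still attends near Day 56. Protocol 9.2.4 says all patients undergo Visit 7, but 6.1 calls the Week 8 visit the end-of-study/withdrawal visit, so this is unclear.
- Nothing is said about expected withdrawals by arm. Treatment failures could cluster on placebo, or AE withdrawals on active drug; the direction of any bias is unknown.

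**Conclusion.** The point holds in this form: the SAP's start-date test, applied to records split as the protocol prescribes, counts an easing pre-dose AE as a TEAE in both e and n, and counts one AE that changes intensity over days several times in e. Each misclassified patient is worth 5.9 percentage points in an arm of 17. The number of such patients cannot be estimated from the documents, and no direction of bias between arms can be claimed.

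The conclusion assumes that the TEAE test is run on each record's own onset date and that the splitting rule survives in Amendment 3. If the eCRF links split rows and the programming uses first onset, easing events drop out. However, a pure first-onset rule would also lose genuine worsening of a pre-dose AE, as the second row of the table shows. The SAP needs explicit wording in either case.

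The absence of an upper limit on the TEAE window does not, on these documents, justify a cut-off at two weeks after last dose or a claim that the comparison favours IBD98-M.

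**What to change.** In SAP 7.9.1:
- Define a TEAE as an AE whose first onset is on or after first dose, or a pre-dose AE whose intensity rises above its last pre-dose level. A record that only continues a pre-dose AE at the same or lower intensity is not a TEAE.
- Link the records of one AE. Count the linked set once in e, at maximum severity, and compute duration from first onset to final stop.
- Confirm in Protocol Amendment 3 that intensity changes over days are still recorded separately, and cite that rule.
- Optionally, flag in the AE listing any event that starts after alternative UC therapy begins. No change to the TEAE window is needed for this.

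The cost is a few lines of SAP text, a link variable and slightly more programming. Data collection and patient conduct do not change, and every record remains in the listings.
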